## 9.3.1. Randomization

Eligible patients with will be randomized in a 1:1 ratio to the intervention vs. control groups, i.e. standard care + convalescent plasma treatment vs. standard care alone. The randomization procedure will be performed electronically through the eCRF (Viedoc). The randomization list will be stratified according to study site (hospital or care home). Block randomization will be used, with block sizes of 4 and 6, in random order.

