## **Objectives and endpoints**

Objectives	Endpoints
Primary	
Assess the effect of convalescent plasma on mortality in COVID-19	Primary endpoint: All-cause mortality within the first 28 days of observation. Secondary endpoints: All-cause mortality within 60 days of observation.
Secondary	
Effect of convalescent plasma on recovery time in patients with active COVID-19 infection	Time from intervention to negative SARS-CoV-2 PCR during a 28 days observation period.
Effect of convalescent plasma on clinical progression of COVID-19 disease	Requirement of oxygen therapy at days 1, 3, 7, 14, 21 and 28 compared to baseline. Change in NEWS score at days 1, 3, 7, 14, 21 and 28 compared to baseline.
Exploratory	
Effect of convalescent plasma on biomarkers in COVID-19	Change in CRP and lymphocyte count at day 1, 3, 7 and 14 after intervention. Time to normalized CRP and lymphocyte count.
Safety of convalescent plasma in COVID-19	Incidence of adverse events.

Brief Summary:	The objective of this study is to evaluate the safety and efficacy of convalescent plasma treatment in symptomatic elderly COVID-19 patients in Norwegian care homes. Approximately 500 eligible participants will randomly
	allocated to either the intervention (Convalescent plasma and standard care) or control (standard care only) group in a 1:1 ratio. Participants will be followed up over a 60-day observation period.
Intervention Group and Duration:	Participants randomized to treatment group will receive convalescent plasma treatment within 2 days after randomization. They will be followed up for 60 days.
Data Monitoring Committee:	Yes
Project leader	[name], Oslo University Hospital
National coordinating institution:	Oslo University Hospital
Study sites:	Study sites are defined as the care home department of participating municipalities
Study monitor:	Clinical trial unit (CTU), Oslo University Hospital
Study setting:	Norwegian care homes for elderly patients in participating municipalities
Inclusion and exclusion criteria	
 
Inclusion criteria
 
1. Age >50 years
 
2. SARS-CoV-2 PCR positive in respiratory tract sample within 3 days before inclusion
 
3. Onset of symptoms within 7 days before intervention as assessed by the attending clinician,
 
4. Voluntary, informed and documented consent by patient or guardian
 

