## 5.2. Exclusion criteria

- 1. Included in any other RCT
- 2. Allergic reactions to plasma products
- 3. Acute severe co-morbidity
- 4. Estimated life-expectancy <90 days prior to COVID-19 as assessed by the attending clinician.
- 5. Other reasons where the attending clinician deems trial participation to be against the best interest of the patient

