## 6.2. Measures to Minimize Bias: Randomization and Blinding

**Sequence:** A randomization sequence will be generated in a computer program and associated with predefined rows of unique patient identification numbers and inserted into the electronic data capture system (EDCS). After the participant has consented the ambulatory team will be informed and will randomize the participant using the EDCS.

Implementation; The randomization list will be produced by the CTU at OUH.

**Blinding:** This is an open-label, randomized controlled trial with a plasma arm administered as a transfusion, and all participants and staff will thus know the intervention to which the patient is allocated.

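### Section 9.3.1 prints the block sizes (4 and 6) in the protocol of an open-label trial with judgement-based entry; they should be held by the CTU, and the stratum they apply to should be clarified

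*Protocol*

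**What the plan says.** Protocol Section 9.3.1 has patients "randomized in a 1:1 ratio to the intervention vs. control groups" through the eCRF. On the restriction it says: "Block randomization will be used, with block sizes of 4 and 6, in random order". On stratification it says: "The randomization list will be stratified according to study site (hospital or care home" (the parenthesis closes there). The synopsis table in Section 1.1 defines a site differently: "Study sites are defined as the care home department of participating municipalities".

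Section 6.2 makes the trial open label, so that "all participants and staff will thus know the intervention to which the patient is allocated". The CTU produces the list and the allocation is drawn electronically: "After the participant has consented the ambulatory team will be informed and will randomize the participant using the EDCS". According to Section 6.3 and the synopsis, the same team gives the transfusion.

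Section 5.2 leaves part of eligibility to judgement. The exclusions include "Estimated life-expectancy <90 days prior to COVID-19 as assessed by the attending clinician" and "Other reasons where the attending clinician deems trial participation to be against the best interest of the patient". Under Section 10.1.2, the principal investigator or a delegated contact at the care home conducts the consent discussion. The primary Cox model in Section 9.3.3 contains treatment and study site only.

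**The concern.** Permuted blocks return to exact balance every 4 or 6 patients. When past allocations are open, the arm that is behind in the stratum is therefore the more likely next one. The electronic list hides the next row, but it does not prevent inference from the rows already revealed. Random ordering of the two sizes does not prevent it either.

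Eligibility and consent are settled before randomisation. If a person who influences them also expects a particular arm, frailer or fitter patients could be put forward selectively. The arms would then differ in prognosis at entry. An objective endpoint such as death gives no protection against that, and the primary model has no prognostic covariate other than site. Printing the block sizes in the document that sites work from makes the inference sharper than it needs to be.

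**Working it through.** The protocol gives no figure for predictability, so there is none to reproduce.

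**Inputs.** Block sizes 4 and 6, 1:1 allocation and stratification by site (Section 9.3.1); open allocations (Section 6.2). Assumption: each block size is equally likely. The protocol says only that the order is random.

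**Step 1: guessing from the running imbalance.** The rule is to guess the arm that is behind and toss a coin at a tie. Expected correct guesses in a block of 2m are m + 2^(2m−1)/C(2m, m) − 1/2.
- Block of 4: 2 + 8/6 − 0.5 = 2.833, or 70.8%.
- Block of 6: 3 + 32/20 − 0.5 = 4.1, or 68.3%.
- Equal mix: (2.833 + 4.1)/10 = 69.3%.

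The rule uses neither the block sizes nor their boundaries. In simulation, an observer who knows the two sizes but not which was drawn, and who guesses optimally, scores the same as this simple rule:

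| Patients in stratum | Correct guesses | Fully certain |
|---|---|---|
| 5 | 64.4% | 4.8% |
| 10 | 68.0% | 6.0% |
| 25 | 68.2% | 6.0% |
| 50 | 69.0% | 5.7% |
| 253 | 69.3% | 5.3% |

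**Step 2: what publishing the sizes adds.** It adds certainty, not a higher average. The simplest case is an imbalance of 3, which can arise only if a block of 6 opens with three of the same arm; the other three are then fixed. That has probability 2/C(6, 3) = 2/20 = 0.1, so it gives 3 × 0.1 = 0.3 certain allocations per block of 6. On average this is 0.3 per 10 patients, or 3%. Other sequences reveal the block too (for example, an imbalance of 2 after four patients in the first block) and bring the total to about 5-6%. An observer who knows the sizes can also call 42-50% of allocations with at least 75% certainty in strata of 10 to 506.

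**Step 3: who sees the sequence.** If several units share one list of 500 patients, in random order of arrival, and each follows only its own running imbalance, the correct-guess rate is 51.5% with 2 units, 51.0% with 5 and 50.4% with 20. The 69% therefore belongs to a person who sees the whole stratum.

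**Step 4: which stratum.** The wording allows at least three readings.
- Each institution has its own list. Its clinicians then see all of it, and the table in Step 1 applies to them.
- Each municipal care home department has one list (synopsis definition). Visibility then depends on how many homes share it.
- There are two strata by type of institution. A single home then sees a small part of a long list and is near 50%.

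**Step 5: other restrictions, for a full-history observer.** Blocks of 4/6/8 give 68.1%, 6/8 give 67.3%, 6/8/10 give 66.5% and 8/10/12 give 65.3%. Larger blocks reduce the guess rate only a little.

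**The case against.** The strongest objection is that the guesser and the decider are different people. The ambulatory team may see the whole sequence, but Section 6.2 informs it only after consent, and no section gives it an eligibility judgement. The attending clinician judges eligibility, and the investigator or a care-home contact takes consent. If the list is shared among homes, a clinician in one of them is near 50%. The room for holding patients back is also narrow: Section 5.1 requires a recent positive PCR and recent symptom onset, and the synopsis has all confirmed cases reported to the principal investigator. This stands, and it limits the concern. It does not remove it, because the protocol does not say what allocation history the principal investigator or the consent-taker sees, and under the first reading in Step 4 the clinician sees the full list.

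Second, randomly varied blocks, a CTU-generated list and electronic allocation after consent are a recognised design. That is right; nothing here is miscalculated. The only feature that needs to change is the disclosure.

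Third, baseline comorbidity is recorded, and an adjusted sensitivity analysis may be in the SAP, which is not available here. That could help after the fact but is no reason to leave the sizes in print.

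**Conclusion.** The point holds as an avoidable weakness. For a person with the full stratum history, about 68-69% of allocations are guessable in strata of ten or more, assuming that the two block sizes are equally likely. Knowing the sizes makes about 5-6% fully certain. For staff with a partial view the rate is close to 50%.

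A reader might infer two stronger things that the documents do not support.
- That publishing the sizes causes the 69%. It does not: the running imbalance alone gives that figure, and hiding the sizes would not lower it.
- That the mortality comparison is biased by a known amount. For a full-history observer who steers at every untied allocation, the false difference would be about 0.75 times the shift in baseline risk on each side: 0 points for no shift, 1.5 for a shift of 2 points and about 3.8 for a shift of 5. The shifts are assumptions without a source in the protocol, and the calculation also requires that the observer controls entry. The documents show neither.

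**What to change.** 1. Delete the block sizes from Section 9.3.1. State instead that the restriction details are held by the CTU in a document not available to investigators, care-home staff or the ambulatory team.
2. For list rows not yet used, have the CTU regenerate the list with undisclosed block sizes, so that the published ones no longer apply.
3. Reconcile the stratification wording in Section 9.3.1 with the site definition in the synopsis, and say which unit has its own list. The study-site covariate in Section 9.3.3 should use the same definition.

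The cost is a short text change, one regenerated list in the existing system and whatever ethics-committee approval Section 10.1.1 requires for the amendment. It needs no extra patients, visits or staff. The gain is also limited: it removes the certainty that comes from knowing the sizes, while the average guess rate for a full-history observer stays at roughly 65-69% under any of the block schemes in Step 5.

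A maximum-tolerated-imbalance scheme is optional. Big stick with limit 3 lowers overall guessing to about 56-58%. However, about 12-16% of allocations become forced, and the mean final imbalance in a stratum rises from about 0.4 to 1.3-1.4. That is a trade-off on which statisticians may differ, and it is not required here.

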## 9.3.2. Analyses Sets

The statistical analyses will be performed on the Full Analysis Set (FAS), which will contain all patients with sufficient data to allow inclusion in the analyses, as randomized. The FAS analyses thereby comply with the intention to treat principle.

A secondary analysis of the primary outcome will be performed on a Per Protocol Set (PPS), where patients who did not receive the entire plasma treatment are excluded.

The FAS and the PPS will be described in detail in the SAP.

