	Randomization and plasma transfusion will take place immediately after enrolment, by an ambulant transfusion team. Blood samples will be taken at day 0, 1, 3, 7 and 14 in the study period. Oropharynx samples will be taken at day 0, 1, 3, 7, 14, 21 and 28 in the study period.	

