# 6.4. Dose Modification

All participants will be evaluated before inclusion and should be eligible for receiving the maximum volume of 300ml plasma. In case of adverse events, transfusion will be terminated, possibly resulting in a dose reduction. The actual dose of the study intervention will then be recorded and these participants will be excluded from the PPS.

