## 7.2. Participant Discontinuation/Withdrawal from the Study

In cases when the patient withdraws his/her consent:

- A participant may withdraw from the study at any time at his/her own request or may be withdrawn at any time at the discretion of the investigator for safety, behavioral, or compliance reasons. This is expected to be uncommon.
- At the time of discontinuing from the study, if possible, an early discontinuation visit should be conducted, as shown in the SoA. See SoA for data to be collected at the time of study discontinuation and follow-up and for any further evaluations that need to be completed.
- The participant will be permanently discontinued from the study at that time.
- If the participant withdraws consent for disclosure of future information, the sponsor may retain and continue to use any data collected before such a withdrawal of consent.

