## 8. Study Assessments and Procedures

## 8.1. Efficacy assessments

*The efficacy of convalescent plasma on the primary endpoint of all-cause mortality* at day 28 will be recorded from the Norwegian death registry.

*The efficacy of convalescent plasma on the secondary endpoint of all-cause mortality* at day 60 will be recorded from the Norwegian death registry.

*The efficacy of convalescent plasma on the secondary endpoint of recovery time* will be assessed by repeated respiratory tract sampling for SARS-CoV-2 PCR analyses at day 1, 3, 7, 14 and 28. The site for sampling as well as the actual sampling technique will be standardized, underscoring the importance of a uniform procedure for all participating centers. Samples will be analyzed at the participating local microbial laboratories adhering to national guidelines for this testing. All samples for a single patient will be tested at the same laboratory to reduce inter-institutional variability. Samples will furthermore be stored for analyses at a core laboratory after the end of the study.

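### The per-protocol rule removes only plasma-arm patients, on events after randomisation, so the secondary per-protocol mortality analysis tends to favour plasma

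*Protocol*

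**What the plan says.** Protocol 9.3.2 gives the primary outcome a secondary analysis on "a Per Protocol Set (PPS), where patients who did not receive the entire plasma treatment are excluded". It states no exclusion for the control arm. Section 6.4 names one route out of the set: "In case of adverse events, transfusion will be terminated, possibly resulting in a dose reduction", followed by "The actual dose of the study intervention will then be recorded and these participants will be excluded from the PPS". Section 9.3.3 confirms the roles: full analysis set (FAS) primary, per-protocol set (PPS) secondary.

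The delay between randomisation and transfusion is described in more than one way. The brief summary in the synopsis says "Participants randomized to treatment group will receive convalescent plasma treatment within 2 days after randomization". The participants' timeframe in the same synopsis says "Randomization and plasma transfusion will take place immediately after enrolment", and 7.1 places the transfusion directly after consent.

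Section 9.3.2 describes the FAS as a set "which will contain all patients with sufficient data to allow inclusion in the analyses, as randomized" and says that it thereby follows intention to treat. All-cause mortality "at day 28 will be recorded from the Norwegian death registry" (8.1), and day-60 mortality has the same source. Section 7.3 seeks vital status for every randomised participant, including those not treated. Details of both sets are left to the SAP.

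**The concern.** A plasma patient who dies before the transfusion team arrives, or whose transfusion is stopped for a reaction, did not receive the entire treatment and leaves the PPS. A control who dies at the same moment, or who is just as frail, has no treatment to miss and stays in. The set is therefore selected in one arm only, on events after randomisation that may be linked to death, and the endpoint analysed on it is death.

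A per-protocol result is usually read as support for the primary result. If it leans towards plasma by selection, it could seem to confirm or strengthen a benefit that randomisation does not show. Deferral to the SAP does not remove the problem, because the exclusion is already fixed in 9.3.2 and 6.4. A SAP that elaborates it keeps the asymmetry, and one that reverses it departs from the protocol.

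**Working it through.** **Inputs.** The protocol attaches no figure to the analysis sets, so the size has to be illustrated. From 9.2: 30% control mortality, 506 patients (253 per arm) and a final two-sided level of 0.048. The design figures reproduce: 4 × (1.960 + 0.842)² / (ln 0.60)² = 120.3, rounded up to 121 deaths; 120.3 / 0.24 = 501.3, rounded up to 502 patients; 502 × 1.008 = 506. The sample size is not in dispute. Delay, hazard shape, share excluded and mortality of those excluded are assumptions.

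**Step 1: deaths before transfusion only, no true effect.** Let survival in both arms be S(t) = exp{−0.357 (t/28)^k}, where 0.357 = −ln 0.70, so 28-day mortality is 30%. Let transfusion time be uniform on 0 to w days. The share of the plasma arm dead before transfusion is q = 1 − (1/w)∫₀ʷ S(u)du. Those patients contribute almost no person-time, so the PPS event-rate ratio, plasma to control, is close to (0.30 − q)/0.30.

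| w (days) | k | q | Dropped of 253 | Rate ratio |
|---|---|---|---|---|
| 2 | 0.6 | 4.46% | 11.3 | 0.85 |
| 2 | 0.8 | 2.36% | 6.0 | 0.92 |
| 2 | 1.0 | 1.26% | 3.2 | 0.96 |
| 2 | 1.5 | 0.27% | 0.7 | 0.99 |
| 0.5 | 0.6 | 1.97% | 5.0 | 0.93 |
| 0.5 | 0.8 | 0.79% | 2.0 | 0.97 |
| 0.5 | 1.0 | 0.32% | 0.8 | 0.99 |
| 0.5 | 1.5 | 0.03% | 0.1 | 1.00 |

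Here k below 1 is a hazard highest at the start, k = 1 is constant and k above 1 is rising.

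**Step 2: any reason for an incomplete transfusion.** Let a share f of the plasma arm be excluded, with mortality m. Plasma mortality in the PPS is (0.30 − f·m)/(1 − f), and the hazard ratio is ln(1 − that value)/ln(0.70). For f = 5% and m = 60%: (0.30 − 0.03)/0.95 = 28.4%, so the hazard ratio is 0.94.

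| f | m = 30% | m = 60% | m = 100% |
|---|---|---|---|
| 2% | 1.00 | 0.98 | 0.94 |
| 5% | 1.00 | 0.94 | 0.86 |
| 10% | 1.00 | 0.87 | 0.71 |

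For the chance of a nominally significant PPS result at 0.048, take the log-rank statistic with mean −ln(HR)·√(D·π₁·π₂), where D is the expected number of deaths and π₁, π₂ are the arm shares. It is 6.5% for f = 5%, m = 60%; 12.5% for f = 10%, m = 60%; and 14.6% for f = 5%, m = 100%.

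**Step 3: the FAS.** With registry vital status for everyone, the share lost is about zero and so is the bias. Even if 2% of one arm alone were lost, the mortality ratio would lie between (0.30 − 0.02)/0.98/0.30 = 0.95 (all of them deaths) and 0.30/0.98/0.30 = 1.02 (all survivors).

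**The case against.** The PPS analysis is secondary. The primary test and the interim stopping test do not use it. If transfusion is immediate, few patients can die first. Nothing in the protocol shows a hazard highest on day 0: the trial enrols early disease and excludes acute severe co-morbidity. Section 2.3 describes transfusion risks as low in frequency. All of this stands. It limits the size and the consequence but does not make the rule symmetric.

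Four stronger readings are tempting, and the documents do not support them.

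- *The FAS also selects on events after randomisation, so the primary analysis is compromised.* No section removes withdrawn patients from the FAS. The statement in 7.2 that "The participant will be permanently discontinued from the study at that time" concerns participation, not analysis sets. Data collected before withdrawal of consent may be used, and a Cox model can censor such patients. Deaths come from the registry. What remains is an undefined data filter that sits badly beside the intention-to-treat statement; it matters more for the PCR, oxygen and NEWS endpoints than for mortality.
- *The PPS excludes every control.* That is the literal wording but plainly not the intention.
- *The PPS is biased towards plasma by construction.* The bias is nil if excluded patients die at the average rate. It is certain only for deaths before transfusion.
- *Exclusions for transfusion reactions add to the bias.* They do so only if those patients die more often than average, and the protocol gives no figure for that.

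**Conclusion.** The point holds for the PPS. The rule in 9.3.2 and 6.4 selects on post-randomisation events in the plasma arm alone, and the resulting mortality comparison favours plasma whenever the excluded patients have above-average mortality. Pre-transfusion deaths alone give an event-rate ratio of about 0.85 to 1.00 under no true effect. The lower end needs a delay spread over the full 2 days and a strongly front-loaded hazard; a short delay or a rising hazard brings it close to 1. Wider exclusions could move it further, but their frequency and mortality are unknown. The effect is confined to a secondary analysis. The primary FAS analysis of mortality is not materially affected, and its definition needs only a wording correction.

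**What to change.** 1. Reword 9.3.2 and the PPS sentence in 6.4 so that PPS exclusions use only criteria that can be applied in both arms, for example major eligibility violations at randomisation. Keep plasma patients who die before or during transfusion in the set.
2. If a treated-only analysis is kept, label it a sensitivity analysis open to selection bias that cannot support the efficacy conclusion. A complier-average estimate is optional. It needs its own assumptions: partial doses do not fit a yes/no compliance variable, and it does not carry over simply to a Cox hazard ratio.
3. Reconcile the statements on the delay from randomisation to transfusion in the synopsis and 7.1.
4. Minor wording: for the mortality endpoints, define the FAS as all randomised patients as randomised, using registry vital status regardless of withdrawal from study procedures. Where consent to registry data is withdrawn, censor the patient at that point.

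The cost is a few reworded sentences and one redefined secondary analysis. No new data are needed.
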